3.1.3. Cohort Doses and Regimens

During the Phase 1b portion of the study, the doses of VRx-3996 and valganciclovir will follow those outlined in [Table 5](#). On Cycle 1 Day 1, in an effort to ensure that patients tolerate oral valganciclovir prior to receiving VRx-3996, valganciclovir will be taken first, followed by VRx-3996 approximately 1 hour later. For all subsequent administrations, the sequence of VRx-3996 and valganciclovir can be dictated by patient convenience (e.g., both drugs may be taken together if tolerated by the patient). With the implementation of Protocol Amendment 4.0, VRx-3996 and valganciclovir are taken together at all timepoints, including Cycle 1 Day 1.

The Safety Review Committee (SRC) ([Section 3.10](#)) will have the option of defining additional cohorts and doses either below, above, or intermediate to the doses listed in [Table 5](#) as needed based on data generated from prior cohorts. The SRC may also define additional cohorts based on alternative dosing schedules (e.g., QD versus BID).

Table 5: Phase 1b Cohort Doses

Cohort Number	Dose VRx-3996**	Dose valganciclovir**
1	10 mg BID (20 mg daily dose)	900 mg BID
2a	5 mg BID (10 mg daily dose)	450 mg BID
2b	10 mg QD (10 mg daily dose)	450 mg BID
2c	10 mg QD (10 mg daily dose)	900 mg QD
3	20 mg QD (20 mg daily dose) [#]	900 mg QD

Abbreviations: *BID* = *bis in die* (twice daily); *PO* = *per os* (oral); *QD* = *quaque die* (once daily); *SRC* = Safety Review Committee

** The Schedule used (e.g., *QD*, *BID*) for either VRx-3996 or valganciclovir may be modified by the SRC as required to accommodate different dosage strengths and patient convenience. However, when the schedule is adjusted, the total daily dose will remain unchanged.

In Cohort 3, VRx-3996 will be administered *PO QD* for 4 days on and 3 days off in a 7-day regimen. The dosing holiday is not considered a dosing hold; if a dose is held for any length of time beyond the 3-day dosing holiday (e.g., dosing does not resume on Cycle 1 Day 8), those subsequent days will constitute a dose hold. Please refer to [Section 3.5 Dose Adjustments/Modifications/Delays](#). If the next dose of VRx-3996 following a dosing holiday (e.g., Cycle 1 Day 8) does not coincide with a scheduled visit, the patient should take the next scheduled dose at home.

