3.2.4. Phase 2 Study Drug(s) Administration Schedule

In the Phase 2 portion of the study VRx-3996 will be administered 20 mg PO QD for 4 days on and 3 days off in a 7-day regimen. Valganciclovir will be administered 900 mg PO QD. VRx-3996 and valganciclovir will be taken at the same time for all visits.

The administration schedule used for VRx-3996 and/or valganciclovir may be modified as appropriate by the SRC during the course of the study. Changes to the schedule will be enacted with minimal or no change in the total daily dose.

If employed during the study, the following schedule definitions will be used:

- QD – Once each day at approximately the same time
- Q12 hours – Twice each day at between a 10 to 14-hour interval
- BID – Twice each day at between 8- and 12-hour intervals (preferably at 12-hour intervals when possible)

The SRC may define and employ other schedules as appropriate based on data accumulated during the course of the study.

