6.4.1. Pharmacokinetics

Phase 1b/2 and Tablet Cohorts

A PK assessment of both VRx-3996 and valganciclovir will be performed following the first administration of VRx-3996/valganciclovir in all patients. The scheduled timepoints are shown in [Table 14](#).

Table 14: Pharmacokinetic Sampling and ECG Schedule for Valganciclovir and VRx-3996

Time	Administration	PK Sampling and ECG Schedule		
Cycle 1 & 2, Day 1		Plasma	ECG	Urine (Cycle 1 only)
Pre-dose***	Meal supplement*	X	X (triplicate)	Void
0 hour	Valganciclovir and VRx-3996			N/A
0.5 hour (± 15 min)		X	X (triplicate)	0–3 hr collection
1 hour (± 15 min)		X	X (triplicate)	
2 hour (± 15 min)		X	X (triplicate)	
4 hour (± 15 min)		X	X (triplicate)	3–8 hr collection
6 hour (± 15 min)		X	X (triplicate)	
8 hour (± 30 min)		X		
Cycle 1 Day 2**				
Pre-dose***	Meal supplement*	X	X (triplicate)	N/A
0 hour	Valganciclovir and VRx-3996			N/A
2 hour (± 15 min)		X	X (triplicate)	N/A
Cycle 1 & 2, Day 15**				
Pre-dose***	Meal supplement*	X	X (triplicate)	N/A
0 hour	Valganciclovir and VRx-3996			N/A
2 hour (± 15 min)		X	X (triplicate)	N/A

* Ensure or equivalent should be consumed prior to dosing. Alternatively, patients may consume a light breakfast in place of consuming an Ensure or equivalent.

** Patients should be reminded not to take their dose at home prior to coming into the clinic on these days. Study visits with PK assessments should occur on days that the patient will take both study drugs, VRx-3996 and valganciclovir.

*** Pre-dose ECG should be conducted prior to meal supplement. If possible, patients should not consume additional food between dose and last ECG timepoint. If 6 hr fasting time for ECGs is not feasible for patients, a high protein, low carb snack immediately following an ECG to maximize the time between food and the next ECG.

At selected sites, urine will be collected for levels of VRx-3996 and its metabolites Cycle 1 Day 1. Patients will be instructed to void urine prior to administration of study drug, then all urine will be collected between 0 and 3 hours, and 3 and 8 hours. Detailed instructions are included in the Study Manual.

Pharmacokinetic analysis will be performed at a central laboratory designated by the Sponsor.

Instructions on the collection, processing, and shipment of patient PK samples for these assays will be provided in the Laboratory Manual.

If available, back-up PK aliquots may be used for future assessment of VRx-3996 metabolites (if identified).

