3.1.1 Phase 1b (Dose Escalation)

During the dose escalation portion of the study, dosing will be based on assigned cohort. Approximately 25 patients are expected to enroll in this phase. Cohort size will be up to 7 patients using a conventional modified 3+3 design for dose escalation studies in oncology.

On Cycle 1 Day 1, in an effort to ensure that patients tolerate oral valganciclovir prior to receiving nanatinostat, valganciclovir will be taken first, followed by nanatinostat approximately 1 hour later. For all subsequent administrations, the sequence of nanatinostat and valganciclovir can be dictated by patient convenience (e.g., both drugs may be taken together if tolerated by the patient). With the implementation of Protocol Amendment 4.0, nanatinostat and valganciclovir will be taken together at all timepoints, including Cycle 1 Day 1.

The first cycle is defined as the dose-limiting toxicity (DLT) assessment period. Grading of DLTs will be according to the National Cancer Institute Common Terminology Criteria for Adverse Events (NCI CTCAE) version 5 and detailed in Section 3.1.5 of the protocol as well as [Section 3.4.1](#) of the SAP. Patients who are unable to complete the DLT assessment period for reasons other than study drug-related toxicity may be replaced if needed to achieve at least 3 patients evaluable for DLTs.

A Safety Review Committee (SRC) comprised of study investigators, the study medical monitor and a Sponsor representative will govern the conduct of the study, and will have the option of defining additional cohorts and doses either below, above, or intermediate to the planned doses as needed based on data generated from prior cohorts. The SRC may also modify the dosing schedule for either nanatinostat or valganciclovir as required to accommodate different dosage strengths and patient convenience. However, when the schedule is adjusted, the total daily dose will remain unchanged. The Phase 1b planned doses for each cohort are provided in Table 2.

Table 2 Phase 1b Dose Levels by Cohort

Cohort Number	Dose Nanatinostat	Dose Valganciclovir
1	10 mg BID (20 mg daily dose)	900 mg BID
2a	5 mg BID (10 mg daily dose)	450 mg BID
2b	10 mg QD (10 mg daily dose)	450 mg BID

Cohort Number	Dose Nanatinostat	Dose Valganciclovir
2c	10 mg QD (10 mg daily dose)	900 mg QD
3	20 mg QD (20 mg daily dose), 4 days on and 3 days off in a 7-day regimen	900 mg QD

BID, twice daily; QD, once daily.

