4.7.3 Plasma Pharmacokinetic Parameters

Plasma concentration-time data will be analyzed by non-compartmental analysis using Base SAS® software, version 9.4 or higher. The following PK parameters will be calculated for nanatinostat and ganciclovir, where data permit:

Table 5 Pharmacokinetic Parameters

C_{\max}	Maximum observed concentration.
T_{\max}	Time of maximum observed concentration.
T_{last}	Time of last measurable concentration
AUC_{0-t}	Area under the concentration-time curve from time 0 to the last measurable observed concentration (C_t), calculated using the linear trapezoidal rule.
$AUC_{0-\infty}$	Area under the concentration-time curve from time 0 extrapolated to infinity, calculated as $[AUC_{0-t} + (C_{\text{last}} / \lambda_z)]$ where C_{last} is the last observed measurable concentration (for Cycle 1 Day 1 only) (if applicable)
AUC_{0-6h}	Area under the concentration-time curve from time 0 to 6 hours (if applicable for nanatinostat)
AUC_{0-7h}	Area under the concentration-time curve from time 0 to 7 hours (if applicable for ganciclovir)
AUC_{0-8h}	Area under the concentration-time curve from time 0 to 8 hours (if applicable for nanatinostat and ganciclovir)
AUC_{0-24h}	Area under the concentration-time curve from time 0 to 24 hours (if applicable)
λ_z	Apparent terminal elimination rate constant, where λ_z is the magnitude of the slope of the linear regression of the log concentration versus time profile during the terminal phase.
$t_{1/2}$	Apparent terminal elimination half-life, calculated as: $\ln(2) / \lambda_z$.
CL/F	Apparent total body clearance, calculated as: Dose / $AUC_{0-\infty}$ for C1D1, and Dose / AUC_{0-24h} for Cycle 2 Day 1.
V_z/F	Apparent volume of distribution during the terminal phase, calculated as: Dose / $[\lambda_z * AUC_{0-\infty}]$ for C1D1, and Dose / $[\lambda_z * AUC_{0-24h}]$ for Cycle 2 Day 1.
$\%AUC_{\text{ext}}$	Percentage of $AUC_{0-\infty}$ due to extrapolation; $AUC_{0-\infty}$, CL/F and V_z/F values on C1D1 will be flagged and excluded from summary statistics where $\%AUC_{\text{ext}} > 20\%$.
$AR_{C_{\max}}$	Accumulation ratio based on C_{\max} between Cycle 2 Day 1 and Cycle 1 Day 1
$AR_{AUC_{0-24h}}$	Accumulation ratio based on AUC_{0-24h} between Cycle 2 Day 1 and Cycle 1 Day 1

Actual sampling times will be used for the estimation of all plasma PK parameters, and all concentrations will be included in the analysis (including concentrations collected outside predefined collection windows).

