4.7.4 Pharmacokinetic Inferential Statistics

The dose proportionality of the key nanatinostat PK parameters C_{max} , $AUC_{0-\infty}$ and AUC_{0-6h} , if appropriate over the administered dose range, will be assessed using the following model using all dose groups:

$$\log(\text{parameter}) = a + b * \log(\text{dose})$$

where 'a' is the intercept and 'b' is the slope. The model will be fit to the pooled, individual group patient data. Parameter estimates of b, including the standard error and 90% CIs will be summarized in a table. If the 90% CI for b includes 1.0, then linearity will be concluded.

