4.9 Changes in the Conduct of the Study or Planned Analyses

The following changes to planned analyses identified within the development of this SAP, relative to the descriptions provided within the clinical study protocol are listed below:

- Section 3.1.3 of the protocol includes a table for intended Phase 1b Cohort Doses.
 - The original intended Valganciclovir dose for Cohort 1 was 900 mg BID, but this was modified per the SRC recommendation after the first

4 patients. The actual Valganciclovir dosing was 900 mg BID for the first 4 patients and then 450 mg BID for the last 3 patients.

- The original intended Nanatinostat dose for Cohort 3 was 20 mg QD. The SRC later recommended to revise this dose to 20 mg QD 4 days per week following review of Cohort 1 safety data.
- Section 3.8 of the protocol states that a central review of patient scans will be performed and may include an assessment based on both Lugano and RECIL criteria. This central review was not performed.
- Section 6.4.1 of the protocol describes urine PK sample collection and, but this was not collected and will not be analyzed.

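### SAP 4.7.3 has no rule ending the Cycle 1 Day 1 profile at the second dose of a twice-daily drug; if the Day 2 pre-dose sample is used, AUC0-inf and half-life are biased upward

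*SAP*

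**What the plan says.** **Regimens.** Cohort 1 takes nanatinostat "10 mg BID (20 mg daily dose") and Cohort 2a "5 mg BID (10 mg daily dose") (protocol 3.1.3, SAP 3.1.1). Valganciclovir is twice daily in Cohorts 1, 2a and 2b. SAP 4.9 confirms that this held for all seven Cohort 1 patients: "The actual Valganciclovir dosing was 900 mg BID for the first 4 patients and then 450 mg BID for the last 3 patients". Protocol 3.2.4 defines BID as "Twice each day at between 8- and 12-hour intervals (preferably at 12-hour intervals when possible").

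**Sampling.** The current Table 14 (protocol 6.4.1) takes plasma on Cycle 1 Day 1 before dosing and at 0.5, 1, 2, 4, 6 and 8 h. The next sample is Cycle 1 Day 2 pre-dose. For Day 2 the instruction is "Patients should be reminded not to take their dose at home prior to coming into the clinic on these days". That holds back the Day 2 morning dose; nothing holds back the Day 1 evening dose.

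**Analysis.** SAP 4.7.3 defines AUC0-t as "Area under the concentration-time curve from time 0 to the last measurable observed concentration", by the linear trapezoidal rule. AUC0-inf adds Clast/lambda-z, and on Cycle 1 Day 1 CL/F is Dose/AUC0-inf. AUC0-24h is planned where applicable, with an accumulation ratio of Cycle 2 Day 1 to Cycle 1 Day 1. The section adds: "Actual sampling times will be used for the estimation of all plasma PK parameters, and all concentrations will be included in the analysis". AUC0-inf, CL/F and Vz/F leave the summaries when more than 20% of AUC0-inf is extrapolated. Under SAP 4.7.1, post-dose values below the quantification limit are set to missing. The SAP does not define *Dose*, gives no rule for choosing lambda-z points, and has no provision for twice-daily drugs.

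**The concern.** With an interval of 8–12 h, a second dose falls between the 8 h sample and the Day 2 pre-dose sample. If the Day 2 value joins the Cycle 1 Day 1 profile, a level produced mainly by the second dose becomes Clast and enters lambda-z as though it came from the first. Separately, a straight line from 8 to 24 h over an exponential decline overstates the area even when there is no second dose.

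PK of both drugs at varying doses is a secondary objective. AUC0-inf is also one of three parameters in the dose-proportionality model of SAP 4.7.4 ("The dose proportionality of the key nanatinostat PK parameters"). If dose there means the single dose, every 5 mg observation comes from a twice-daily cohort. A schedule-dependent artefact could then be read as a dose effect or as a difference in clearance between cohorts.

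**Working it through.** The plan states no figure to reproduce, so the SAP rules were applied to a known profile.

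**Inputs.** Nanatinostat half-life 1.8 h (protocol 1.8). AUC0-inf 111 ng·h/mL at 10 mg (protocol Table 4), used only for scale. Sampling times from the current Table 14, with Day 2 pre-dose at 24 h. Second dose at 10 or 12 h. Assumed: one compartment and ka = 2/h. With k = ln 2/1.8 = 0.385/h, Tmax = ln(2/0.385)/(2 − 0.385) = 1.0 h, matching the documented median.

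**Model.** C(t) = AUC·k·ka/(ka − k)·(e^(−kt) − e^(−ka·t)), plus the same curve shifted by the dose interval.
- C(8) = 111 × 0.477 × e^(−3.08) = 2.43 ng/mL.
- C(24) = 0.005 ng/mL with no second dose, 0.246 with one at 10 h, 0.526 with one at 12 h.
- AUC0-8h by the linear rule = 104.7 ng·h/mL.
- First-dose area beyond 8 h: 2.43/0.385 = 6.3, so the true total is 111.

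**SAP rules with the 24 h value included.** The 8–24 h trapezoid is 8 × (C8 + C24). Lambda-z uses the last three or four points.

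| Second dose | 8–24 h area | Half-life, h | Tail | AUC0-inf | Ratio to 111 |
|---|---|---|---|---|---|
| none | 19.5 | 1.80 | 0.0 | 124.2 | 1.12 |
| 10 h | 21.4 | 3.9–4.3 | 1.4–1.5 | 127.5–127.6 | 1.15 |
| 12 h | 23.6 | 5.1–6.0 | 3.9–4.6 | 132.2–132.9 | 1.19–1.20 |

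Most of the area excess is therefore the linear rule (+12% with no second dose). The half-life error is due entirely to the second dose. The tail is 1–3% of AUC0-inf, so the 20% filter does not catch these values.

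**CL/F.** With *Dose* as the single dose, CL/F is 1/1.20 to 1/1.15 = 0.84–0.87 of the truth. With the daily dose it is twice that, 1.67–1.74.

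**AUC0-24h as actual exposure.** Two doses deliver about 221 ng·h/mL over 24 h. The SAP line gives 104.7 + 21.4 = 126.1 or 104.7 + 23.6 = 128.3, which is 0.57–0.58 of it, because the line skips the second peak.

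**Ganciclovir.** The documents give no half-life; 3–5 h is an assumption.

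| Half-life | Ratio, 10 h (extrapolated) | Ratio, 12 h (extrapolated) | Once daily, linear |
|---|---|---|---|
| 3 h | 1.35–1.36 (8–9%) | 1.50–1.55 (15–17%) | 1.16 |
| 4 h | 1.53–1.57 (18–20%) | 1.80–1.90 (27–31%) | 1.14 |
| 5 h | 1.76–1.84 (29–32%) | 2.14–2.36 (39–45%) | 1.11 |

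For the once-daily column, linear-up/log-down is within about 2% of the truth.

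**After the fix.** Profile ended at 8 h, half-life 1.8 h: 104.7 + 6.3 = 111.0, ratio 1.00, half-life 1.80 h, 6% extrapolated. Log-down without ending the profile is not enough. With the second dose at 12 h the 8–24 h area is 16 × (2.43 − 0.526)/ln(2.43/0.526) = 19.9, still far above 6.3.

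**The case against.** The strongest reply is that the SAP never places the Day 2 sample in the Cycle 1 Day 1 profile. SAP 4.7.2 describes the serial profile as Cycle 1 Day 1, and Table 14 lists Day 2 as a separate block. The sentence about including all concentrations goes on to speak of samples outside their collection windows, so it does not clearly pool days. AUC0-24h is also used for Cycle 2 Day 1, where Table 14 has no next-day sample, so its presence does not prove that the Day 2 draw is used. All of this stands: the bias is conditional. It does not supply the missing rule. AUC0-24h is planned on Cycle 1 Day 1, and the only observed value near 24 h is the Day 2 one.

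The sampling schedule of the twice-daily cohorts is also unknown. SAP 4.7.2 points to Table 14 across protocol versions, and the planned AUC0-6h and AUC0-7h suggest that earlier profiles ended there. This stands too, but it would not help: without the 8 h sample the nanatinostat AUC0-inf ratio rises to 1.33–1.37 (1.30 with no second dose).

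A 24 h value below the quantification limit is set to missing and the bias disappears. No limit is given, and the modelled level is only 0.25–0.53 ng/mL at 10 mg BID, about half that at 5 mg. However, the evening dose raises the 24 h level 48- to 103-fold, so twice-daily patients are the ones more likely to keep the point.

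Two stronger readings are tempting. One is that ganciclovir AUC0-inf would be reported at up to 2.4 times the truth. The 20% filter removes every 5 h case and the 4 h cases with a 12 h interval from the AUC0-inf and CL/F summaries. It does not remove half-life. The other is that every AUC is overstated. AUC0-24h as actual twice-daily exposure is understated.

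**Conclusion.** The point holds in conditional form. SAP 4.7.3 does not say which samples form the Cycle 1 Day 1 profile or where the profile of a twice-daily drug ends, and its stated rules give wrong values if the Day 2 pre-dose sample is used and quantifiable. For nanatinostat at 1.8 h, AUC0-inf is then about 15–20% high and half-life reads 3.9–6.0 h. CL/F is about 13–16% low, but only if *Dose* means the single dose. In once-daily patients with a quantifiable 24 h value, the linear rule alone adds about 11–16% at assumed half-lives of 3–5 h.

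These sizes rest on one-compartment kinetics, ka of 2/h, an evening dose taken at 10–12 h, and the current Table 14. The documents do not support saying that the bias will occur.

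The reach is limited: secondary, descriptive PK, with the second-dose effect confined to twice-daily drugs in Phase 1b. The Phase 2 and tablet regimens are once daily. Cmax and AUC0-6h, the other two dose-proportionality parameters, and AUC0-8h are unaffected by the second dose. With assumed cohort sizes, the AUC0-inf slope would shift by about −0.10 to −0.14, against a 90% CI half-width of about 0.24–0.59 at coefficients of variation of 57–138%. The shift is real but seldom decisive. The correction is worth making because it costs little.

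**What to change.** In SAP 4.7.3:
- List the samples that form the Cycle 1 Day 1 profile. For a drug given twice daily, end it at the last sample before the second dose.
- For such a drug, exclude Day 2 pre-dose from lambda-z, AUC0-t and AUC0-inf, and do not report AUC0-24h from a line across the second dose.
- Replace the linear rule by linear-up/log-down, and list this in SAP 4.9 as a change from protocol 12.4.1.
- Define *Dose* in CL/F and Vz/F as the single administered dose.

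The cost is SAP wording and a software setting. Fewer twice-daily patients will have a reportable AUC0-24h or AUC0-inf: with the profile ended at 8 h, about 28% is extrapolated at a 4 h half-life and 36% at 5 h, so the 20% filter would apply. AUC0-6h and AUC0-8h, already planned, remain available for comparison across schedules.

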No formal statistical analysis will be performed to compare cohorts. This study is exploratory in nature; descriptive statistics will be tabulated by study phase and cohort and reviewed to evaluate all study endpoints.

4.1.2 *Summarization by Visit*

In general, data summarized by study visit will be based on the nominal, scheduled visit label as reported on the eCRF. Data collected for the last patient visit will be summarized separately and this summary will be labeled as “End of Treatment” in the analysis.

For laboratory data summaries, data summarized by study visit will be based on the nominal, scheduled visit label as reported on the eCRF when available. If the scheduled visit is not available, then all data collection, including unscheduled and early

termination visits, will be reassigned a study visit based on the actual days relative to baseline using the visit windows identified in [Table 3](#) below.

Table 3 Visit Windows for Analysis

Scheduled Visit	Target Study Day	Study Day Interval
Baseline	0	≤ 0
Cycle 1 Day 1	1	1
Cycle 1 Day 2*	2	2
Cycle 1 Day 8	8	3 – 11
Cycle 1 Day 15	15	12 – 18
Cycle 1 Day 22	22	19 – XX^{**}
Cycle 2 Day 1	$XX + 1$	$XX + 1$
Cycle 2 Day 8	$XX + 8$	$(XX + 2) – (XX + 11)$
<hr/>		
...		

*Note Cycle 1 is the only cycle with a schedule Day 2 visit

** Day 22 is the last scheduled visit within each cycle, and the end of the study interval (XX) is calculated as the day before the start of the subsequent cycle.

If more than one value is mapped to the same visit, the value collected closest to the target study day will be considered for summarization. If two values collected on different days are mapped to the same scheduled visit and are equidistant from the target study day, the earlier of the values will be considered. The visit displayed on subject data listings will be reflective of the scheduled visit label as reported on the eCRF. Study days relative to baseline will be displayed for each visit to indicate to which visit the assessment may have been reassigned, if any.

Otherwise, data collected at unscheduled visits will not be included in by-visit summaries but will be considered when endpoint derivations potentially include multiple visits (e.g., determination of baseline value, determination of worst post-baseline value, etc.). All data will be included in patient listings.

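### Cycle 2 Day 1 clearance, volume and the AUC accumulation ratio are defined on a 24-hour area, but Cycle 2 Day 1 sampling ends at 8 hours and no rule covers the gap

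*SAP*

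**What the plan says.** SAP Section 4.7.3 opens its parameter list with "The following PK parameters will be calculated for nanatinostat and ganciclovir, where data permit". In Table 5:

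- AUC0-24h is "Area under the concentration-time curve from time 0 to 24 hours (if applicable"), with no rule for completing it when sampling stops early.
- C2D1 CL/F is given as "and Dose / AUC_{0-24h} for Cycle 2 Day 1". Vz/F on that day divides by the same area times lambda-z.
- The AUC ratio is the "Accumulation ratio based on AUC_{0-24h} between Cycle 2 Day 1 and Cycle 1 Day 1".
- AUC0-t is "calculated using the linear trapezoidal rule". Extrapolation with lambda-z is described only for AUC0-∞, on C1D1 only. The rule that excludes values with more than 20% extrapolated area also covers C1D1 only.
- AUC0-8h is listed for both drugs but is not used in the ratio or in C2D1 clearance.

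On sampling, Protocol Table 14 (Section 6.4.1) takes plasma pre-dose and at 0.5, 1, 2, 4, 6 and 8 h on Day 1 of Cycles 1 and 2. The only sample near 24 h is the Cycle 1 Day 2 pre-dose draw. Protocol Table 15 has only Days 1 and 15 in Cycle 2, and a note to SAP Table 3 confirms that "Cycle 1 is the only cycle with a schedule Day 2 visit". SAP Section 4.7.2 plans C2D1 profiles for all tablet patients and some Phase 2 capsule patients.

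Nanatinostat at the RP2D is given "4 days on and 3 days off in a 7-day regimen".

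**The concern.** The SAP names three C2D1 outputs that need concentrations out to 24 h, and the design does not collect them. A programmer must either leave the outputs blank or choose a way to fill 8–24 h. Nothing in the SAP says that this choice must be the same on both days. Only C1D1 has a later sample, so the easiest mismatch sets a 24 h area on C1D1 against an 8 h area on C2D1. That mismatch pushes the ratio below 1 and pushes C2D1 CL/F up. It could be read as falling exposure or rising clearance on repeat dosing.

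There is also a question of interpretation. For nanatinostat at the RP2D, an on-schedule C2D1 dose follows three drug-free days, so a comparison "between Cycle 2 Day 1 and Cycle 1 Day 1" cannot measure accumulation. PK of both drugs is a secondary objective.

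**Working it through.** The plan states no figure here to reproduce. The check is a noise-free one-compartment oral model sampled at the Table 14 times.

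**Inputs.** Nanatinostat half-life is 1.8 h median, range 1.1–7.8 h, with median Tmax 1 h (Protocol 1.8). Ganciclovir Tmax is set at 2 h, inside the 1–3 h of Protocol 1.9. Its half-life is not in the documents and is assumed to be 3–6 h. Areas use the linear trapezoidal rule.

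**Formula.** C(t) ∝ exp(−ke·t) − exp(−ka·t), with ke = ln 2 / half-life and ka set to give the stated Tmax.

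**Nanatinostat, half-life 1.8 h, same profile on both days.** As fractions of Cmax, the values at 0, 0.5, 1, 2, 4, 6 and 8 h are 0, 0.847, 1, 0.807, 0.387, 0.179 and 0.083. At 24 h the value is 0.0002.

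- Linear AUC0-8h = 0.212 + 0.462 + 0.904 + 1.194 + 0.566 + 0.262 = 3.60.
- The single 8–24 h trapezoid on C1D1 = 16 × (0.083 + 0.0002)/2 = 0.665, so C1D1 AUC0-24h = 4.26. The model's true AUC0-24h is 3.82.
- Mismatched ratio = 3.60/4.26 = 0.84, against a true 1.00.
- Decomposition: truncation gives 3.60/3.82 = 0.94, a loss of about 6%. The wide trapezoid gives 4.26/3.82 = 1.12, inflating C1D1 by 12%. Then 0.94/1.12 = 0.84.
- At half-lives of 1.1 and 7.8 h, the ends of the reported range, the ratio is 0.95 and 0.53.

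**Handling of the 24 h nanatinostat value.** At 0.02% of Cmax it is probably below quantification (the limit is not given). SAP 4.7.1 sets such values to zero if pre-dose and to missing if post-dose, and the Cycle 1 Day 2 pre-dose sample is both. Treated as missing, both days end at 8 h and the ratio is 1.00. Treated as zero, it stays at 0.84.

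**Ganciclovir.** The same mismatch, with half-lives in hours:

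| Quantity | 3 | 4 | 5 | 6 |
|---|---|---|---|---|
| Ratio, same profile both days (true 1.00) | 0.66 | 0.61 | 0.58 | 0.55 |
| Ratio, daily dosing to steady state | 0.67 | 0.63 | 0.60 | 0.59 |
| True AUC0-24h ratio at steady state | 1.01 | 1.02 | 1.04 | 1.07 |
| C2D1 area captured by 8 h | 0.78 | 0.71 | 0.65 | 0.60 |

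**C2D1 CL/F from an area cut at 8 h** is overstated 1.06-fold for nanatinostat at 1.8 h, and 1.28- to 1.66-fold for ganciclovir at 3–6 h.

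**Alternatives.**

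- Completing only C2D1 with lambda-z, while C1D1 keeps its 24 h sample, gives 0.89 for nanatinostat at 1.8 h. Ganciclovir at steady state gives 0.85–0.97, still below the truth.
- Lambda-z completion on both days recovers the true ratio for both drugs.
- AUC0-8h on both days gives 1.00 for nanatinostat and 1.01, 1.02, 1.05 and 1.08 for ganciclovir at 3, 4, 5 and 6 h.
- Using the C2D1 pre-dose level as the 24 h level recovers the true ganciclovir ratio under steady daily dosing.

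**Carry-over of nanatinostat.** On schedule, the last Cycle 1 dose is Day 25 and C2D1 is Day 29, 96 h apart. Even at 7.8 h the residual fraction is 2^(−96/7.8) ≈ 0.0002.

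**The case against.** The strongest reply is that the SAP does not prescribe the mismatch. An area cut at 8 h already has its own names in Table 5 (AUC0-8h, or AUC0-t), so entering it as AUC0-24h would breach the SAP's own definition. The qualifiers on applicability and data availability would then leave the C2D1 outputs unreported: a gap, not a false result. This stands. A reader might infer that the plan will report a fall in exposure. The documents support only that it could, and only if the two days are completed differently.

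A reader might also infer that C2D1 AUC0-24h is beyond reach. It is not. Table 5 already needs lambda-z on C2D1 for Vz/F, so completion from that profile is feasible. For once-daily ganciclovir the C2D1 pre-dose level could stand in for the 24 h level. The SAP states neither route. The second cannot serve nanatinostat after three days off.

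A third tempting inference is that Dose/AUC0-24h is the wrong formula for nanatinostat because C2D1 is not at steady state. After washout at a half-life of 1.8 h, AUC0-24h is 99.99% of AUC0-∞, so the formula would give nearly the true CL/F. It departs only at the extreme (88% at 7.8 h). The fault is the missing area, not the formula.

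Finally, the outputs are descriptive and accumulation is not a named objective. The Cmax ratio is unaffected, and dose proportionality does not use AUC0-24h. All of this limits the consequence. It does not supply the missing rule.

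**Conclusion.** The conflict is real: three C2D1 outputs are defined on an area that the sampling does not cover, and the SAP neither completes it nor names a substitute. Read strictly, the outputs cannot be produced. Read loosely, unlike areas may be compared.

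In the loose case, with no true change, the ratio is 0.84 for nanatinostat at the median half-life. Less than half of that shortfall is truncation. The larger part is the wide C1D1 trapezoid, and the bias disappears if the 24 h value is below quantification and treated as missing. For ganciclovir the ratio is about 0.55–0.66, mostly from truncation. That figure rests on the assumed 3–6 h half-life. All sizes rest on a one-compartment model without noise.

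Separately, the nanatinostat ratio at the RP2D measures change between occasions rather than accumulation, provided visits keep to schedule. The primary endpoints are untouched. This should be corrected before analysis, but it is confined to secondary, descriptive PK.

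**What to change.** Amend SAP Section 4.7.3:

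1. Base the AUC accumulation ratio on AUC0-8h, which is already in Table 5 and sampled on both days.
2. Report C2D1 CL/F and Vz/F only if AUC0-24h is completed by one stated rule: that profile's own lambda-z or, for once-daily ganciclovir, the C2D1 pre-dose level as the 24 h level. Extend the 20% extrapolation limit to C2D1. Otherwise omit both parameters.
3. If an AUC0-24h ratio is kept, apply the same 8–24 h rule on both days, and state how a Cycle 1 Day 2 pre-dose value below quantification is handled.
4. Describe the nanatinostat ratio as between-occasion change.

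The cost is wording only, with no new samples. The ratio will cover only the first 8 h. Two further consequences follow for ganciclovir at a 3–6 h half-life. Completion with lambda-z would extrapolate 22–40% of the area (1 − 0.78 to 1 − 0.60), so the 20% limit would exclude most such values. The pre-dose route avoids that, but its single linear 8–24 h trapezoid overstates the area 1.18- to 1.10-fold, leaving CL/F at 1/1.18 = 0.85 to 1/1.10 = 0.91 of its true value. Omitting these parameters may be the simpler choice.
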